Elimination of HCV was recently formulated as a WHO target and was set for the year 2030. Globally, approximately 6.2% of HIV-infected patients are co-infected with HCV. Of the patients living with HIV, people who inject drugs (PWID) and men who have sex with men (MSM) are at particularly high risk of HCV co-infection. However, as a result of the early adaptation of opioid substitution and needle exchange programs in the Netherlands, the number of PWID co-infected with HIV and HCV is limited. This is unfortunately not the case for HIV-infected MSM. Until recently, the prevalence of chronic HCV in Dutch HIV+MSM was very high at 4.8% (compared with 0.2% in the Dutch population in general). However, after the restrictions on the use of direct-acting antivirals against HCV (DAA) were lifted in 2015, the prevalence of chronic HCV in HIV+MSM decreased rapidly. With this decreasing prevalence of chronic HCV a decrease in the *incidence* of *acute* HCV infections in Dutch HIV+MSM was observed as well. Indeed, while the incidence of *acute* HCV in HIV+MSM in care in the Netherlands was 1.1% in 2014, this decreased by 51% in 2016. However, no further decline in the number of *acute* HCV infections was observed in 2017. Also, the incidence of HCV *re*-infections in HIV+MSM that were cured of a previous HCV infection continues to be very high in the DAA era with reported rates varying between 5-10% per year.

The continuously high *re*-infection risk and the lack of a further decline in the HCV incidence after 2016 illustrates that universal DAA therapy for all patients diagnosed with a chronic HCV infection on its own will not result in HCV elimination. Other interventions are needed to reach the WHO goal of HCV elimination by 2030. One of these additional interventions may be decreasing the time to diagnosis of HCV *re*-infections in order to decrease the duration that these *re*-infected patients may transmit their HCV to sex partners. Indeed, if the diagnosis of HCV *re*-infection is made earlier, counseling on transmission risk in combination with the prompt initiation of HCV therapy will prevent transmission to sex partners and prevent new HCV infections on the population level.

The study we describe here was designed to evaluate the effect and feasibility of more frequent and home-based testing for HCV on the time to diagnosis and treatment of HCV *re*-infections.

Objective:

To assess the effectiveness of HCV RNA self-testing in reducing the time to diagnosis of HCV *re*-infection in MSM previously cured of an HCV infection, compared to the current diagnostic standard of care.

To evaluate whether the uptake of self-testing is sufficient and warrants the use of HCV RNA self-testing in clinical practice.

Study design:

Prospective controlled intervention trial. MSM cured of an HCV infection who are at continued risk for an HCV *re*-infection (based on the results of a short questionnaire, APPENDIX B) are offered HCV RNA self-testing and asked to use the test every 6 months for 2 consecutive years.

Study population:

225 to 250 adult MSM cured of HCV from 10-15 HIV and PREP clinics in the Netherlands and Belgium.

Intervention:

Eligible patients are instructed on the use of a capillary blood self-collection kit. They receive 2 kits per year for 2 consecutive years to allow them to send plasma to the virology lab of the Erasmus MC every 6 months by regular post mail.

Primary endpoints:

Comparison of the time to HCV *re*-infection diagnosis in patients using the HCV RNA self-test (intervention) with the time to HCV *re*-infection diagnosis with the standard diagnostic approach (control) in the modified intention to treat population.

Secondary endpoints:

1. Comparison of the time to HCV *re*-infection diagnosis in patients using the HCV RNA self-test (intervention) with the time to HCV *re*-infection diagnosis with the standard diagnostic approach (control) *in the subpopulation that has sent in all planned self-tests during their entire follow-up* (per protocol analysis).
2. Of the HIV+MSM that were offered to participate in the study, the percentage that accepted to participate *and* eventually self-collected and sent in at least one plasma sample in each 12-month period of study participation.

3. Overall incidence of HCV *re*-infection in the entire study population regardless of the type HCV diagnostic test that was used.

4. Number of screen failures as a result of a positive HCV-RNA test at the screening visit.

Nature and extent of the burden and risks associated with participation, benefit and group relatedness:

The burden associated with participation in the study consists of taking a finger prick blood sample for the self-test 4 times in 2 years and sending the sample to the laboratory by regular post mail. No costs will have to be made for mailing the sample. Capillary finger-prick blood sampling is used as a standard diagnostic test for many diseases (e.g. glucose monitoring in diabetes) and is associated with a negligible risk. The study may potentially be beneficial for those participants in which an HCV re-infection is diagnosed as they will be referred for counselling and HCV therapy which has the potential to prevent transmission to sex partners.

1. INTRODUCTION AND RATIONALE

Viral hepatitis was the seventh leading cause of death worldwide in 2013, increasing from the tenth leading cause in 2010 (1). The vast majority of morbidity and mortality attributable to viral hepatitis is due to hepatitis C virus (HCV) and hepatitis B Virus (HBV). In response to this increasing public health challenge, the World Health Organization recently released targets for HBV and HCV elimination by 2030 (2). Elimination is traditionally defined as a reduction to zero in the incidence of disease in a specific population or geographical location, with continued prevention efforts required to prevent the re-establishment of transmission (3).

Because a strict definition of elimination would require substantial economic and political resources and could be unattainable in most settings, the goal of “elimination” is often flexibly defined. The recent WHO elimination “as a public health threat” targets are comprised of a 90% relative reduction in new infections and a 65% relative reduction in hepatitis-related mortality by 2030. Hence, to achieve the WHO incidence elimination targets, efforts must focus on both prevention of disease and prevention of transmission. The advent of highly effective HCV direct acting antiviral (DAA) therapy, with cure rates (also called sustained viral response, SVR) of 95% or higher has renewed optimism that substantial reductions or elimination of end stage liver disease and HCV-related mortality is a possibility. The WHO strategy does not include a discussion relating to elimination of viral hepatitis among HIV-infected populations specifically but given the shared transmission routes many people living with HIV are coinfected with viral hepatitis as well. Globally, approximately 6.2% (3.4% to 11.9%) of HIV-infected (HIV+) patients are also coinfected with HCV, equating to approximately 2.28 million (IQR 1.27 to 4.42) HIV/HCV coinfected individuals (4). The burden of HIV/HCV coinfection is particularly high in people who inject drugs (PWID) and among men who have sex with men (MSM). However, in the Netherlands, the early adoption of opioid substitution and needle exchange programs has limited the number of PWID coinfected with HIV and HCV.

Regarding the epidemiology of HCV in HIV+MSM, it has been estimated that globally 6.4% of them are coinfected with HCV (4). Indeed, in contrast to the lack of sexual HCV transmission among heterosexual couples, HCV transmission readily occurs among MSM during anal sex. Therefore, it comes as no surprise that before restrictions on the use of DAA therapy were lifted in the Netherlands, the prevalence of HCV in Dutch HIV+MSM was equally high at 4.8% (5). Furthermore, not only the prevalence, but also the incidence of HCV in Dutch HIV+MSM is substantial. In 2014, 99 of the 8849 or 1.1% of HIV+MSM in care in the 19 largest HIV centers spread across the Netherlands, were diagnosed (5). This high

prevalence *and* incidence is in sharp contrast with the very low overall prevalence of HCV in the Dutch population in general (0.2%), which is one of the lowest worldwide (6, 7). Therefore, if the Netherlands wants to achieve the WHO hepatitis elimination goals, it is opportune to aim for HCV elimination in population subgroups with a high HCV prevalence rather than the entire Dutch population. Because the large majority of the HIV infected MSM in the Netherlands is aware of their HIV infection and in care in one of the Dutch HIV treatment centers, this specific HCV risk group is already identified. Also, 98% of them consented to have their data used for research purposes by the Stichting HIV monitoring (SHM) as part of the ATHENA cohort. Therefore, reliable and up-to-date data on the number of HIV+MSM ever diagnosed with or treated for HCV are available, and these data are truly representative of the entire Dutch HIV+MSM population. The importance of the SHM data registry regarding the HCV epidemiology in HIV+ patients is well illustrated by several recent studies. In 2018, Boerekamps et al. used SHM data to measure the impact of the introduction of unrestricted DAA therapy in the Netherlands as of November 2015 on the prevalence of HCV among HIV+ patients (8). The study showed that just 15 months after the reimbursement restrictions on DAA therapy were lifted, already 82% of HCV coinfected patients were cured or receiving DAA therapy. In MSM this was even higher at 89%. Furthermore, because patients cured of HCV can no longer transmit HCV to their partner, it was anticipated that this rapid treatment uptake would result in a decrease in new (incident) HCV infections as well. This was indeed observed as the rapid uptake of DAA therapy in HIV+MSM was followed by a 51% decrease in new (=acute) HCV infections in 2016 (9). These interesting observations have been welcomed with enthusiasm in the HIV-HCV coinfection research community as an example of “HCV microelimination” and an exemplary first step towards HCV elimination in general (10, 11).

For all the reasons described above, we consider it unlikely that, even in HIV+ MSM in the Netherlands, HCV elimination will be possible if no additional interventions are implemented. Therefore, we designed 3 studies of which the common goal is to provide policy makers, physicians and patients with data that can help in choosing the most effective interventions needed to eliminate HCV in men who have sex with men.

The 3 studies consist of

1. A phylogenetic study; By sequencing a large number of viruses from patients diagnosed with a prevalent or incident HCV infection, we hope to get a better picture on current transmission networks in order to identify the source of incident HCV infections in MSM in Dutch patients. This will be a study in collaboration with the Academic Medical Center in Amsterdam and HCV researchers from outside the Netherlands.
2. An HCV prevalence study; This study will measure the prevalence of undiagnosed HCV in HIV *negative* MSM visiting the sexually transmitted diseases GGD clinic in order to evaluate the usefulness of systematic screening for HCV of HIV negative MSM attending STD clinics in the Netherlands.
3. An HCV *re*-infection study; In this study we will evaluate if HCV RNA self-testing can significantly decrease the time to diagnosis of an HCV *re*-infection. The study will include MSM previously cured of an HCV. If a substantial decrease in the time to diagnosis and

therefore also the time to “awareness” and the time to the initiation of HCV therapy and cure is achievable, this will limit onward transmission and prevent new HCV infections. This study is described below.

INTRODUCTION TO STUDY NR.3.

As previously mentioned, the HCV *re*-infection rate in HIV+MSM is very high due to ongoing risk behavior. In a prospective case-control study, Vanhommerig et al. identified several risk factors for acquiring an HCV infection. These were receptive unprotected anal intercourse, sharing sex toys, unprotected fisting, injecting drugs during sex, sharing straws when snorting drugs, having a lower CD4 cell count and having a recent diagnosis of ulcerative sexually transmitted infection (19). Various studies report on *re*-infections following SVR in HIV+MSM, but the incidence estimates have a considerable range, which could be explained by differences in study populations regarding risk behaviors, harm reduction interventions and background viremic prevalence (15). In a retrospective study in 606 previously HCV infected HIV+MSM from Austria, France, Germany and the UK, a *re*-infection incidence of 7.3/100 person-years was reported (14). In a smaller Dutch study from the pre-DAA era, Lambers et al. found a much higher HCV *re*-infection incidence of 15.2/100 person-years in 56 HIV+MSM in the Netherlands (20). Consequently, it is clear that HIV+MSM with a previously cured HCV infection have an increased risk of acquiring a new HCV infection. At the moment, HIV+MSM with a previously cured HCV infection undergo ALT testing approximately twice a year during their regular HIV outpatient clinic visit. If an ALT elevation is observed an HCV RNA test is performed to exclude or confirm a new HCV infection. However, in acute and chronic HCV infections ALT is not always elevated. ALT levels correlate with the duration of HCV infection, the viral load and the presence of periportal bridging/necrosis and it has been estimated that up to 25% (range 10 to 40%) of patients with chronic hepatitis C infection have persistently normal aminotransferase levels (21). Given these factors, using an HCV RNA as well as increasing the frequency of ALT testing both have the potential to shorten the time to diagnosis of an HCV *re*-infection significantly. If this is indeed the case, a shorter time to diagnosis (and treatment) will also reduce the time that a patient is at risk of transmitting HCV to others. Therefore, it may be one of the additional steps that is needed towards the elimination of HCV.

2. OBJECTIVES

The main objective of this study is to demonstrate that the use of a HCV RNA self-test will be an effective and feasible way to decrease the time to diagnosis of an HCV *re*-infection. If this is indeed the case, interventions to prevent HCV transmission to sex partners (e.g. counseling, initiation of DAA treatment) can be initiated sooner after an HCV *re*-infection.

For this purpose, patients will be offered to be trained in capillary blood sampling and separation of plasma at home and will send the plasma sample, by regular post mail, to a central lab for HCV RNA testing. The HCV RNA self-test will be done twice yearly on top of the standard of care ALT testing policy that is also done twice a year at the HIV outpatient clinic. Therefore, patients in the study will undergo HCV testing 4 times a year; twice a year with ALT testing during their regular HIV outpatient clinic visit (followed by an HCV RNA test if the ALT turns out to be elevated) and twice a year with the home-based HCV RNA test. This self-test is done in between the HIV outpatient clinic visits (figure 1).

Primary objective

1. Measure if and to what extent HCV RNA self-testing decreases the time from HCV re-infection to diagnosis compared with the current standard of care.

Secondary objectives:

1. Measure the uptake and acceptability of HCV RNA self-testing in MSM cured of an HCV.
2. Measure the incidence of HCV re-infection in MSM in the Netherlands and Belgium in 2018-2019-2020.

3. STUDY DESIGN

Single arm open label multicenter study.

We consider a single arm open label multicenter study the most appropriate design, given the relatively small patient population at risk for HCV re-infection in the Netherlands. Indeed, the number of HIV+MSM that fulfill the in- and exclusion criteria (see below) in the participating Dutch study centers is estimated at 250-350, of which a subset will be interested in study participation. Three additional Belgian study centers and one Swiss center have also agreed to participate in the study. Even with the participation of these foreign HIV treatment centers, a randomized fully powered study remains unachievable. Indeed, if the time to diagnosis would be reduced from 4.5 to 2.5 months with the intervention and assuming a standard deviation of 2 and an 80% power and alfa of 5%, the study would need to include 2 groups of patients in which a minimum of 16 re-infections would be diagnosed in each group (see sample size calculation below). With an incidence of HCV re-infections of $\pm 8\%$ during the 2 years of follow-up this would mean that 2×200 patients need to be included to diagnose 2×16 re-infections. As our most optimistic inclusion scenario will allow recruitment of 250

patients in 2 years, this means that a single arm study with 200 patients will already take 4 years to complete given the follow-up time of 2 years of each of the patients. Therefore, we consider a single arm open label multicenter study the most appropriate.

For the purpose of the analysis, we will use the study population as its own “virtual” control group (see below for a more detailed explanation of this control group).

[figure not shown]
Intervention:

The self-test that is used to detect HCV RNA is performed every 6 months on top of standard of care ALT test as described above. The HCV RNA testing will be done at home by the patient 3 months after each HIV outpatient clinic visit and sends the plasma sample to our laboratory by regular post mail. If HCV RNA is detected, the treating physician will be informed and the patient contacted immediately and invited to visit the outpatient clinic for confirmation of the positive HCV RNA self-test and evaluation of liver enzymes. If the presence of HCV RNA is confirmed, HCV therapy can then be initiated according to the Dutch or Belgian HCV treatment guideline.

Standard HCV diagnostic procedures in the “virtual control group”:

The standard of care HCV re-infection diagnostic strategy used by HIV outpatient clinics is measuring ALT levels every 6-months. If an ALT elevation is documented, HCV RNA testing is performed to diagnose a potential HCV re-infection. If this HCV RNA test is positive, HCV therapy can then be initiated according to the Dutch HCV treatment guideline.

Figure 1 illustrates the timing of the home-based HCV RNA test in the intervention group; The self-test is done every 6 months in between the ALT tests at the outpatient HIV clinic. Furthermore, the self-test is done at the screening visit as well to exclude that patients with an undiagnosed HCV infection are included.

Figure 1.

Defining the time to diagnosis in the intervention and the virtual control group:

Patients diagnosed with an HCV re-infection by the HCV RNA self-test are contacted immediately by the site investigator and invited to visit the outpatient clinic to have their liver enzymes tested and to confirm the HCV diagnosis with a whole blood HCV RNA PCR test. If at that time the ALT level is elevated, we will assume that an HCV RNA test would have been done by the treating physician at the next 6-monthly HIV outpatient clinic visit (in \pm 3 months) and therefore the HCV diagnosis would have been made at that time point.

In patients diagnosed with an HCV re-infection in which the ALT level turns out to be normal, we will assume that the ALT level would *not be elevated* at the next planned HIV outpatient visit (in general \pm 3 months later), but that it *would be elevated* at the consecutive HIV outpatient clinic visit (in general \pm 9 months later) and therefore the HCV diagnosis would have been made at that time point. This conservative approach that assumes an ALT elevation in all patients 9 months after the positive HCV RNA test is needed because we anticipate that all patients will have started HCV therapy within 6 months after diagnosis and this leads to prompt ALT normalization. Therefore, we cannot use the actual measured ALT level 9 months after the positive HCV RNA test.

[figure not shown]
The date of infection is estimated as the midpoint between the date of last negative HCV test and the date of the first positive HCV test. The last negative HCV test can be either a negative ALT test or a negative HCV RNA test. The first positive HCV test can be either a positive HCV RNA self-test or a positive whole blood HCV RNA test performed in the hospital. This estimation of the date of infection will be used for the analysis of the time to diagnosis in both the intervention and the virtual control group.

This is illustrated by the following example and in figure 2. A study patient with a positive HCV RNA self-test 9 months after the start of the study had an ALT within the normal range at 6 months. When he is informed about the positive self-test and the positive test is confirmed by the local investigator his ALT is measured as well and turns out to be elevated. For this patient, the date of infection is estimated at 7.5 months ($6+((9-6)/2)$). The actual time to re-infection diagnosis in the intervention arm is (9-7.5) or 1.5 month. To evaluate the time to re-infection diagnosis as part of the “virtual” control group, we will disregard the result of the self-test at 9 months and assume that at 12 months an elevated ALT would have been detected, because his ALT was also elevated at 9 months. Therefore, the virtual time to re-infection diagnosis for this patient is (12-7.5) or 4.5 months (scenario 1 in figure 2). However, if the ALT level of this patient would have been normal at 9 months, the virtual time to re-infection diagnosis would be different. Indeed, while the actual time to re-infection diagnosis would still be 1.5 month, the virtual time to re-infection diagnosis would be (18-7.5) and therefore 10.5 months because we will assume that ALT would still be normal at the 12 months HIV outpatient clinic visit but would have become elevated at the next consecutive HIV outpatient clinic visit at 18 months (scenario 2 in figure 2).

[figure not shown]
Please note that all patients will undergo an HCV RNA self-test at the time of screening for the study. This will not only allow for the demonstration of the self-test by the trial-nurse but will also ascertain that patients with an undiagnosed chronic HCV are not included.

Figure 2

Scenario 1

Scenario 2

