4. STUDY POPULATION

4.1 Population (base)

Study population:

Only patients that provide written informed consent will be included. They will first have to review the instruction video that explains and shows how the capillary blood collection and separation of plasma should be done. If the patient is still willing to participate after he has seen the instruction video and received all information by the research team, he will receive the self-testing kit with all materials needed to send in 4 plasma samples over a period of 2 years. The patients will be offered HCV RNA self-testing for 2 consecutive years and thus during 400 patient years of follow-up. Recruitment will stop when at least 1 plasma sample is received from 200 patients. Therefore, we estimate that we will need to include 225 to 250 patients to have an evaluable population of at least 200.

We allow HIV+ as well as HIV- MSM to be included as long as they fulfill the in- and exclusion criteria. HIV negative MSM can only be included if they are taking PREP and if HCV RNA testing is not done as the standard of care HCV diagnostic strategy at the PREP clinic but ALT testing is done as an HCV testing policy no more often than 3x/years. Twice yearly testing is the standard of care in HIV+ patients in the Netherlands but the frequency may be higher or lower in HIV uninfected PREP users per local policy (e.g. in Belgium).

The total number of patients that was informed about the study and the number of patients that reviewed the video but who never actually started using the HCV RNA self-test will be used to evaluate the acceptability of HCV RNA self-testing.

For the statistical analysis the following populations are defined:

Modified Intention to treat population (MITT):

All patients who signed the informed consent, received the HCV RNA self-test kit and in which the HCV RNA test at the screening visit was negative.

Per protocol population (PP):

All patients who signed the informed consent, received the HCV RNA self-test kit and in which the HCV RNA test at the screening visit was negative and who collected all 6 monthly plasma samples during the entire follow-up.

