4.3 Exclusion criteria

A potential subject who meets any of the following criteria will be excluded from participation in this study:

- Age < 18
- Patients that are tested by HCV RNA as a standard of care test (e.g. in the context of PREP use) > 1x/year
- Patients that are expected to be tested by ALT at their HIV or PREP clinic <1x/year

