4.4 Sample size calculation

200 HIV+MSM with a previously cured or a spontaneously resolved HCV infection will be included. These patients will be offered HCV RNA self-testing for 2 years and thus during at least 400 patient years of follow-up.

Previous reports on the incidence of HCV re-infection have observed a re-infection incidence of 5 to 15% per year. However, we should also consider that after the roll-out of DAA therapy in the Netherlands a 51% decrease in the number of acute HCV infections was observed in 2016 compared with 2014. Therefore, we estimate that the incidence of re-infection will be 4% rather than 5-15% per year. Therefore, we anticipate to diagnose a HCV re-infection in 8% of the patients during the 2 years of follow-up. With the inclusion of 200 patients and an average follow-up of 2 years per patient, we should therefore be able to diagnose 16 re-infections. The calculator for a continuous outcome superiority trial of the website sealedenvelope.com was used for the sample size calculation because the outcome we measure is continuous (days).. Now assuming a time from re-infection to diagnosis of 4.5 months or 135 days (SD of 2 months or 60 days) with the current standard of care ALT testing strategy (virtual control group) and a reduction to 2.5 months or 75 days with the HCV RNA self-testing intervention, the required sample size is 16 infections per arm. Because these 16 infections will be used to calculate the time to diagnosis for the intervention as well as for the control group, a sample size of only 16 infections will give the study 80% power to show a difference between the intervention and the virtual control group.

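### Men with yearly routine clinic HCV RNA are eligible, but the virtual control can date a diagnosis only through ALT; for some of their normal-ALT infections this credits self-testing with too large a gain, a minor bias of unknown size

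*Combined protocol and SAP*

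**What the plan says.** Section 3 defines the comparator: "The standard of care HCV re-infection diagnostic strategy used by HIV outpatient clinics is measuring ALT levels every 6-months". HCV RNA follows only if ALT is raised. For a man with a positive self-test, the ALT taken at the confirmation visit fixes his virtual diagnosis date.

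- If ALT is raised, "we will assume that an HCV RNA test would have been done by the treating physician at the next 6-monthly HIV outpatient clinic visit", about 3 months later.
- If ALT is normal, the plan supposes that it stays normal at the next visit but that "it *would be elevated* at the consecutive HIV outpatient clinic visit (in general \pm 9 months later". In the worked example, "the virtual time to re-infection diagnosis would be (18-7.5) and therefore 10.5 months", against an actual 1.5 months.

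Section 3 lets a hospital RNA result serve as the first positive test, and a negative RNA serve as the last negative test. Neither Section 3 nor Section 10 lets a scheduled routine RNA set the virtual date.

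On eligibility, Section 4.3 excludes "Patients that are tested by HCV RNA as a standard of care test (e.g. in the context of PREP use) > 1x/year". A man tested exactly once a year is not excluded. Section 4.1 is stricter for HIV-negative PrEP users, who may enter only "if HCV RNA testing is not done as the standard of care HCV diagnostic strategy at the PREP clinic". That condition does not bind HIV-positive men.

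The primary objective in Section 2 is a comparison with the current standard of care. Section 10 puts the focus on the size of the reduction, with at least 2 months regarded as clinically relevant.

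**The concern.** For an HIV-positive man with yearly clinic RNA, the care he actually receives includes a test that finds the infection whatever his ALT. The dating rule ignores that test. A routine RNA can move his estimated infection date, by serving as the last negative test, but it can never move his virtual diagnosis date.

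An additional test cannot delay a diagnosis, so wherever the rule is wrong for these men it makes the comparator too slow. The error falls on the cases credited with a 9-month gain, which weigh most in the mean. With 16 re-infections expected, and if all were self-test diagnoses, re-dating one case from 9 to 3 months would move the mean by 6/16 = 0.375 months.

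**Working it through.** **Inputs from the documents**

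- Self-tests at months 3, 9, 15 and 21, and clinic visits at 6, 12, 18 and 24 (Section 8.3 table).
- Virtual diagnosis 3 months after the self-test if ALT is raised, 9 months after if normal (Section 3).
- Share with normal ALT, p: Section 1 says "up to 25% (range 10 to 40%) of patients with chronic hepatitis C infection have persistently normal aminotransferase levels". This describes persistently normal ALT in chronic infection. The rule needs the share with normal ALT at the work-up of a recent re-infection, so 25% (10–40%) is only a proxy.
- Share of men on yearly clinic RNA, q: not given. Shown from 10% to 100%.

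**Assumption.** Two clinic visits a year, with routine RNA at one of them.

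**Step 1: the plan's own figures.** In the worked example, infection is placed at 7.5 months and the self-test is at 9. Raised ALT gives 12 − 7.5 = 4.5 months (gain 12 − 9 = 3). Normal ALT gives 18 − 7.5 = 10.5 months (gain 18 − 9 = 9). Both agree with Section 3.

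The sample size also reproduces. Section 4.4 works by "assuming a time from re-infection to diagnosis of 4.5 months or 135 days (SD of 2 months or 60 days" and a reduction to 75 days. Then 2 × (1.960 + 0.842)² × (60/60)² = 15.70, rounded up to 16 per arm, with power 80.7%. The present point does not affect this.

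**Step 2: when yearly RNA would come first (normal ALT).**

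| Routine RNA at months | Self-tests at which the virtual time falls from 10.5 to 4.5 months | Self-tests at which 10.5 months stands |
|---|---|---|
| 12, 24 | 9, 21 | 3, 15 |
| 6, 18 | 3, 15 | 9, 21 |

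Half the self-test dates are affected. The gain there falls from 9 to 3 months, so the average gain for a normal-ALT case in such a man is (3 + 9)/2 = 6 months instead of 9.

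**Step 3: mean gain among self-test diagnoses.**

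- Under the plan: 3(1 − p) + 9p = 3 + 6p. At p = 25% this is 4.5 months.
- With yearly RNA taken into account: 3 + 6p − 3pq.
- Overstatement: 3pq.

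| q | Overstatement, p = 25% (months) | Mean gain, p = 25% (months) | Overstatement, p = 10% to 40% (months) |
|---|---|---|---|
| 10% | 0.075 | 4.43 | 0.03 to 0.12 |
| 25% | 0.19 | 4.31 | 0.075 to 0.30 |
| 50% | 0.375 | 4.13 | 0.15 to 0.60 |
| 100% | 0.75 | 3.75 | 0.30 to 1.20 |

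**Step 4: effect on the conclusions.** At q = 100% the mean gain is 3 + 3p: 3.3, 3.75 and 4.2 months at p = 10%, 25% and 40%, all above 2. Every paired difference for a self-test diagnosis is still at least 3 months, so all signs stay positive and the Wilcoxon signed rank statistic does not change.

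**Step 5: a different timing assumption.** If RNA dates were spread evenly over the year, 75% of normal-ALT delays would be shortened, by 3.375 months on average over all normal-ALT cases. At p = 25% and q = 100% these cases contribute an overstatement of 0.25 × 3.375 = 0.84 months, close to the visit-aligned 0.75.

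**The case against.** **The affected group may be empty.** Sections 1, 2 and 3 describe HIV-clinic care as six-monthly ALT with RNA only after an elevation. The Section 8.3 table lists no routine RNA at the clinic visits, and the only example in the Section 4.3 criterion is PrEP use. An eligibility ceiling is not evidence that yearly-RNA men will be enrolled. This stands: q is unknown and could be near zero.

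**The control is a defined strategy.** Section 10 labels it as the ALT-based strategy, so it need not follow each man's own care. This has some force, but the objective in Section 2 is stated against current care. Section 3 also already lets hospital RNA set the infection date and the actual diagnosis date.

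**There is an opposing bias.** A man whose ALT stays normal, and who has no routine RNA, is credited with a control diagnosis at +9 months that ALT would not have triggered. That is true, but it concerns other men. Where RNA is done at a yearly visit, it falls at +3 or +9 months in any case, so the +9 date is not generous to the control.

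**A reader might infer that the 2-month conclusion is at risk.** That needs two further assumptions. Suppose half of all MITT infections are first found at the clinic and count as zero difference. At p = 25% the overall mean is then 0.5 × (4.5 − 0.75q): 2.25 months at q = 0, 2.06 at q = 50% and 1.88 at q = 100%. It falls below 2 only if q exceeds two thirds. Nothing in the documents supports that share.

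**Conclusion.** The point holds as a minor, one-directional bias in the estimated size of the reduction. It is clearest for HIV-positive men with yearly routine RNA and normal ALT at work-up. If RNA is done at one of two yearly visits, about half of their virtual dates are 6 months too late.

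With p = 25%, the overstatement among self-test diagnoses runs from 0.075 months (q = 10%) to 0.75 months (q = 100%). These figures rest on the visit-aligned timing, on a normal-ALT share borrowed from chronic infection, and on a q that the documents do not give.

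Two further readings go too far. Not every 9-month delay in these men is wrong, because in half of the cases the routine RNA falls at the +9-month visit and the credited date is right. The 0.75 months is also not a trial-level figure unless every man has yearly RNA. The sample size and the signed-rank result are unaffected, and the mean gain among self-test diagnoses stays above 2 months.

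**What to change.** Record for each man at enrolment whether his clinic does routine HCV RNA and when it is next due. In the Section 3 dating rule, set the virtual diagnosis date to the earlier of (a) the ALT-based date and (b) the next clinic visit at which his routine RNA was due. Report the ALT-only date as a sensitivity analysis, and state how many re-infected men had yearly RNA, so that the reader can see q.

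The cost is small. RNA frequency must already be checked for Section 4.3, so the due month is the one additional CRF item, and the rule gains one sentence. The credited reduction may be slightly smaller. The change should be made before results are seen, because the study is open label and the dating of a handful of cases should not be left to later judgement.
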